1. Hypothesis and Specific Aims

Overarching Hypothesis: Insulin signaling is a critical neurobiological substrate of anhedonia in mood disorders

Specific Hypotheses: In individuals with mood disorders, objective and self-reported measures of anhedonia and reward behaviors are associated with alterations in insulin signaling-related molecular, cellular and neural substrates. Considering the role of insulin in the regulation of energy expenditure, we primarily hypothesize that individuals with mood disorders will display decreased willingness to make effort for rewards, relative to healthy controls; and that this abnormality will be associated with:

- a) Molecular: Differential gene and protein expression of the metabolic (i.e. PI3K/Akt) and mitogenic (i.e. Ras/MAP kinase) components of the insulin signaling pathway, as well as with components of reward-related processes (i.e. dopamine receptors and transporter)
- b) Physiology: Reduced peripheral sensitivity to insulin and corresponding metabolic correlates, including increased body mass index and dyslipidemia (i.e. peripheral insulin resistance)
- c) Neural Circuits: Diminished response to insulin in cortico-striatal networks (i.e. brain insulin resistance)

Overarching Aim: To determine the role of insulin signaling on the neurobiological substrates subserving anhedonia within individuals with mood disorders.

Specific Aims:

- a) Molecular: Assessment of components of the insulin cascade, as well as of anhedonia and reward-related processes, using a proteomics and gene expression approach;
- b) Physiology: Measurement of peripheral sensitivity to insulin and metabolic correlates, including body mass index and dyslipidemia;
- c) Neural Circuits: Evaluation of the insulin sensitivity of prefrontal (e.g. prefrontal cortex) and striatal (e.g. nucleus accumbens, ventral tegmental area) networks in the resting-state and during an effort-based decision making test, using acutely administered intranasal insulin and functional magnetic resonance imaging (fMRI);
- d) Behavioral: Measurement of willingness to make effort for rewards, as well as of other components of reward response and anhedonia, using validated behavioral tasks and clinical scales (e.g. Snaith-Hamilton Pleasure Scale SHPS).

2. Background and Rationale

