Biomarkers: High sensitivity CRP and TNF α will be measured at both visits (hs-CRP only). Ultrasensitive ELISA will be used to measure high-sensitivity CRP and TNF- α , TNF-RI and TNF-R2 (measured at both visits). For exploratory mechanistic analysis, a 10-plex immunoassay of

inflammatory cytokines will be measured at both visits (e.g. IFN- γ , IL-1 β , IL-2, IL-4, IL-6, IL-8, IL-10, IL-12p70, IL-13). Blood will be collected after a 12 hour fast and centrifuged at 1000g for 15 min at 4°C; plasma will be stored at -80 °C.

Behavioral assessment: These tasks are simple, user-friendly tools that provide an opportunity, when used in conjunction with the most widely used questionnaires, to gain novel insights on reward behaviors in mood disorders.

- a) The primary behavioral measurement will be effort-based decision-making, assessed using the Effort-Expenditure for Rewards Task (EEfRT)³³, which will be done in a fMRI paradigm⁷³, as described below during Visits 2 and 3.
- b) Assessments will include the validated anhedonia scale Snaith-Hamilton Pleasure Scale (SHPS), the mood questionnaires Montgomery-Åsberg Depression Rating Scale (MADRS) and Young Mania Rating Scale (YMRS) during each study visit, and the Bandit Task during the first visit.

Neural Circuits Assessment: A promising tool to study the effect of insulin on CNS is intranasal insulin, which is delivered directly into the brain, without relevant effects on peripheral glucose^{76,77}. A single dose of intranasal insulin has been shown to influence brain activation, increasing regional perfusion and functional connectivity between the hippocampus and the PFC⁷⁸⁻⁸⁰. Acute administration of intranasal in randomized, placebo-controlled, cross-over designs has been previously used to determine regional responses to insulin in the resting-state or during tasks^{78,80}.

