After screening and baseline assessment, participants will receive a crossover treatment assignment of either insulin or diluent followed by an MRI scan, with a washout period of 1 week. Therefore, participants will receive a total of 2 MRI scans throughout the course of the study- one following the first treatment, and one following the second treatment. The subsample will be enriched for the presence of self-reported anhedonia, using a score of greater than 2 on the SHPS as a cut-off, which provides the best discrimination between "normal" and "abnormal" level of hedonic tone⁸¹. This subsample will also have equal representation of normal weight and obese participants.

To proxy insulin activity within pre-selected brain regions, we will use a provocation paradigm, involving the administration of exogenous intranasal insulin, based on the published work of other research groups research groups Activation of brain regions will be assessed during the resting state and task-based reward paradigm (i.e. EEfRT), following an intranasal administration of either 160 units of intranasal insulin or diluent (insulin and placebo will be prepared as nasal sprays), in a randomized, double-blinded, cross-over design. Please refer to the pharmacy manual for randomization details. A hypothesis-driven region of interest approach will be used to investigate initially the striatum and the medial PFC (mPFC). Willingness to make effort for rewards will be measured with the EEfRT³³. Briefly, participants have to select between an easy and a hard task. Both tasks involve pressing a key for a predetermined amount of time. The hard task offers more money (variable amounts), but is harder and takes twice as long. Participants make their selection knowingly under different win probabilities (i.e. they might not win money even if they are successful if the win probabilities are low). This task will measure proportions of hard-task choices with varying probabilities of reward and reward magnitudes. To provide stable estimations, the fMRI task will be conducted in three runs⁷³.

Table 1

Assessment	Baseline (V1)	First Spray (V2)	Second Spray (V3)		
General Information					
Demographics	✓				
Questionnaire					
Medical Comorbidity	✓				
Questionnaire					
Family Psychiatric	✓				
History					
Questionnaire	,				
SES Questionnaire	√				
MRI Questionnaire	✓	✓	✓		
Anthropometric Measures					
Height (ft)	✓				
Weight (kg)	✓	✓	✓		
Blood Pressure	✓	✓	✓		
(mmHg)					

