This procedure is repeated until the required number of nasal spray bottles has been prepared. Once completed, the nasal spray bottles are wiped with 70% isopropyl alcohol soaked gauge and removed from the laminar flow hood and appropriately labeled.

Both active and placebo nasal spray bottles are kept separate from each other and a worksheet will be completed to document information, including date of preparation, batch #, expiry date, drug name and strength. The IV certified pharmacy technician who has prepared the dose is responsible for completing the documentation and will be affixing the labels identifying what was prepared. The labels, at a minimum, will contain information regarding the lot #, strength, date of manufacture, expiry date, and storage conditions. All of this will be verified by a pharmacist.

Labeling

All labels will contain product name, volume, protocol number, investigational drug warning, dosage instructions, storage conditions, lot number, expiration date, and the pharmacy name.

Storage

Please refer to the pharmacy manual for information on storage.

Study Medication Administration

This will be a single-dose, randomized, double-blinded, cross-over study involving intranasal insulin/placebo solution.

Designated pharmacy staff will dispense study medication, in a double-blind manner, according to the randomization code specific to each subject and dosing period.

Details regarding intranasal insulin and diluent can be referred to in the pharmacy manual.

The investigator and/or designee will instruct the study participant on how the intranasal insulin/placebo spray should be administered. Each study participant is to receive a single dose of Humulin R 160 U / placebo.

- Given:
 - The nasal spray bottles provide a deliverable volume of 0.1 mL/spray.
 - o Humulin R insulin will be sourced as 100 units/mL in a vials of 10 mL from Eli Lilly.
 - o Diluent will be sourced as 10 mL/vial from Eli Lilly.
- Each spray will offer:
 - o 0.1 mL (i.e., 10 units) of Humulin R insulin
 - o 0.1 mL of diluent (to serve as placebo)
- To obtain a dose Humulin R 160 U / placebo
 - o 16 sprays (0.1 mL/spray) are to be given per dose

- o This works out to 16 sprays split between each nostril such that each nostril receives 8 sprays.
- The sprays will be administered between alternating nostrils.

Given this is a crossover study, the study participants will receive a total of two doses in this study. The time between 2 doses is one week.

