4.3 Disposition of Used/Unused Product

Please refer to the pharmacy manual for information on the disposition of used/unused product.

5. Methods of Assigning Subjects to Treatment Groups

Please refer to the pharmacy manual for information on the methods of assigning subjects to treatment groups (i.e. randomization, and blinking/masking).

6. Analytic Plan, Power Analysis and Approach to Potential Challenges

Initial data analyses will inspect socio-demographic and clinical group differences as well as correlations between clinical and biological variables and specified behavioral measures. Clinical or demographic variables demonstrating a correlation with both biological and behavioral measures, will be assessed as potential confounders⁸². The EEfRT behavioral data will be analyzed using generalized estimating equation (GEE) models, according to previous studies^{30,33}. For the assessment of associations between the remaining behavioral measurements and biometric data, we will use generalized linear models, due to its greater flexibility and ability to analyze data with non-normal distributions. Group (mood disorders vs. non-psychiatric) effects will be analyzed, with age, gender, and other relevant covariates included in the models. Special considerations will be given to smoking and use psychotropic medications, given its potential effects of both reward processes and insulin signaling.

Mediation and moderation models will be assessed using regression-based, bias-corrected bootstrap tests⁸³. The main objective is to test whether there is a mediated effect of X (i.e. mood disorders) on the outcome Y (i.e. anhedonia and reward behavior) through M (i.e. insulin signaling and dopamine metabolism). If appropriate, moderated mediation models (conditional process analysis) will be used to test whether the mediation effect was contingent on a moderating variable W (e.g. obesity, medications). This method uses bootstrapping to determine bias-corrected (asymmetric) 95% confidence intervals for the indirect effects⁸⁴. Bootstrapping methods have been recently advocated, as they are based on random sampling of the data and do not make assumptions about the shape of the sampling distribution; they are also more powerful and allow for the construction of more accurate confidence intervals, relative to normal theory methods⁸³.

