For the imaging analysis, statistical parametric mapping (SPM8, Wellcome Department of Cognitive Neurology, London, U.K., www.fil.ion.ucl.ac.uk/spm) will be used to preprocess the raw fMRI data. A hypothesis-driven region of interest approach will be used to investigate initially the striatum and mPFC. For the resting-state data, BOLD signal in these regions will be compared between conditions (i.e. insulin and placebo) for each subject using GEE. For the task-based data, mean percent BOLD signal change in these regions under varying reward and probability conditions will be extracted, and we will compute a set of contrasts testing the main effects of reward magnitude, reward probability, and the interaction for each subject⁷³. These first-level individual contrast maps will be fed into a second-level group (i.e. mood disorders vs. controls) and condition analysis, which will also use GEE. Association between behavioral measurements, biometric data and neuroimaging measurements will be assessed with generalized linear models. The false discovery rate (FDR) method will be used to correct for multiple comparisons and significance will be taken at a FDR-corrected threshold of p < 0.05^{86} .

Power Analysis: The primary hypothesis of this study is that anhedonic symptoms in individuals with mood disorders will be mediated by abnormalities in insulin signaling; therefore, the power analysis is based on a bias-corrected bootstrap test of mediation. Results from our preliminary data indicated that the path coefficients were mostly of medium effect sizes (e.g. $\beta \approx 0.25$ -0.35); empirical analysis indicated that in this condition a sample sizes of 116 is necessary to achieve 80% power85. To account for the possibility of subject attrition and/or inadequate measurements, we will set an initial enrollment goal of 150 subjects.

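### No Visit 2/3 model names the group-by-condition interaction that hypothesis (c) needs, the resting-state model leaves group out, and none has a period term

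*Combined protocol and SAP*

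**What the plan says.** Section 1, hypothesis (c), expects "Diminished response to insulin in cortico-striatal networks (i.e. brain insulin resistance" in people with mood disorders; the comparator in that section is healthy controls. Aim (c) covers both the resting state and the effort task.

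Section 3 describes a two-period crossover of intranasal insulin and diluent in 25 patients and 25 controls. The EEfRT is done "as described below during Visits 2 and 3". Imaging is assessed "during the resting state and task-based reward paradigm (i.e. EEfRT), following an intranasal administration". On spacing, Section 4.1 says: "The time between 2 doses is one week".

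Section 6 gives the models:

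- **Resting state:** "For the resting-state data, BOLD signal in these regions will be compared between conditions (i.e. insulin and placebo) for each subject using GEE".
- **Task fMRI:** subject-level contrasts go into a "second-level group (i.e. mood disorders vs. controls) and condition analysis, which will also use GEE". The only interaction named is reward magnitude by reward probability, within subject.
- **EEfRT behaviour:** "The EEfRT behavioral data will be analyzed using generalized estimating equation (GEE) models, according to previous studies". The same paragraph adds: "Group (mood disorders vs. non-psychiatric) effects will be analyzed, with age, gender, and other relevant covariates included in the models".

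No model has a period or sequence term. Randomization is left to the pharmacy manual, which the document cites for assignment and masking, not for the analysis.

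**The concern.** A response to insulin is insulin minus placebo. Saying that it is diminished in patients compares that difference between two groups. The model term that does this is group x condition, and none of the Visit 2/3 models states it.

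The gap differs by outcome.

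- **Resting state:** a factor that (c) requires is absent. A significant result would show that insulin changes the signal, not that patients respond less. The resting-state part of (c) could then be reported as supported without having been tested.
- **Task fMRI:** both factors are named, so the interaction is at most implied.
- **EEfRT:** this is under-specification, not a stated decision to drop condition. Every EEfRT session follows a spray, so a group effect from a model without condition averages an insulin and a placebo session.
- **Period:** the same scan and task are repeated a week apart, so a practice or familiarity effect is plausible. No model allows for one.

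**Working it through.** **Inputs.** From the document: 25 patients and 25 controls (Section 3); 116 and 150 participants (Section 6, Power Analysis); FDR-corrected significance at 0.05 (Section 6). The only power figure in the plan is 116 for 80% power on the mediation test, so there is no stated figure for the insulin-placebo contrast to reproduce. The following are assumptions: response sizes, in SD units of the within-person insulin-placebo difference; two-sided unadjusted 0.05; equal group sizes at 116 (58 v 58) and 150 (75 v 75).

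**Step 1. What the resting-state test detects.** With complete data, comparing conditions over everyone amounts to testing whether the mean difference score is zero. If controls respond by r_C and patients by r_P in equal numbers, the mean is (r_C + r_P)/2 and the pooled SD is √(1 + ((r_C − r_P)/2)²). The noncentrality at n = 50 is mean × √50 / SD.

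- 0.5 and 0.5: 0.5 × 7.071 / 1 = 3.54
- 0.5 and 0.25: 0.375 × 7.071 / 1.008 = 2.63

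Simulation of difference scores (40,000 replicates) gives:

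| Controls / patients | (c) is | Condition test significant |
|---|---|---|
| 0.5 / 0.5 | false | 93% |
| 0.5 / 0.25 | true | 74% |
| 0.6 / 0.6 | false | 99% |
| 0.6 / 0.3 | true | 87% |

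For a given control response, the test is positive more often when (c) is false. The interaction test rejects in 5% of trials in the 0.5 / 0.5 case.

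**Step 2. What the interaction test can detect.** It is a two-sample comparison of difference scores, with SE √(2/n) for n per group. Noncentral-t solutions for 80% power:

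| Split | Interaction, 0.05 | Interaction, 0.0125 (illustrative) | Condition effect, 0.05 | Interaction power, 0.5 v 0.25 |
|---|---|---|---|---|
| 25 v 25 | 0.81 | 0.98 | 0.40 | 14% |
| 58 v 58 | 0.52 | 0.63 | 0.26 | 27% |
| 75 v 75 | 0.46 | 0.55 | 0.23 | 33% |

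The normal approximation agrees: at 25 v 25, (1.960 + 0.842) × √(2/25) = 0.79.

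**Step 3. EEfRT averaging.** Let D_plc and D_ins be the patient-control differences in the placebo and insulin sessions. The averaged group effect is (D_plc + D_ins)/2 = D_plc + (D_ins − D_plc)/2, that is, the placebo-session difference plus half the behavioural interaction. Hypothesis (c) is neural and does not itself imply a behavioural interaction, so results by condition are needed to see whether there is one.

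**Step 4. Period.** With balanced sequences, an unmodelled period effect π (same SD units) multiplies the SE by √(1 + π²). That is 3% for π = 0.25, 12% for 0.5 and 41% for 1.0. Simulated power at 25 v 25 for an interaction of 0.81 (20,000 replicates):

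| π | 0 | 0.1 | 0.2 | 0.3 | 0.5 | 0.8 |
|---|---|---|---|---|---|---|
| Without period | 80% | 79% | 78% | 77% | 71% | 59% |
| With period | 79% | 79% | 79% | 79% | 79% | 79% |

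The interaction is biased only if sequences are unbalanced between groups. A 13/12 v 12/13 split gives a bias of (26/25 − 1) − (24/25 − 1) = 0.08 times π. A 15/10 v 10/15 split gives 0.40 times π.

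**The case against.** **Other analyses bear on (c).** Section 1 words (c) as a correlate of the effort deficit, and Section 6 plans behaviour-imaging associations and a mediation model whose first path compares groups on the mediator. But the mediator is described only as insulin signaling and dopamine metabolism, never as the insulin-placebo difference in these regions. An association between behaviour and imaging does not show that patients respond less than controls. The gap remains.

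**The resting-state sentence may describe only a first-level step.** It compares conditions within each subject, and the group-level sentence comes later. However, that sentence takes up the contrast maps just described for the task, and nothing similar follows for rest. Extending the general group-effects sentence to imaging would add a group main effect, not the interaction.

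**The 93% is not a type I error rate.** This stands: the condition test is then correctly detecting a real insulin effect. The problem arises only if that result is read as support for (c), and the plan offers no other resting-state test that could be.

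**The larger sample sizes are weakly grounded.** This also stands in part. The 116 and 150 come from the mediation calculation, and no patient-control split is given for them. With 150 split 100 v 50 the detectable interaction is 0.49, and with 125 v 25 it is 0.62, instead of 0.46.

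**Period is minor.** Largely right: below about 0.3 SD the loss is negligible, and the document gives no period-effect size. The term is ordinary crossover practice and secondary to the missing interaction.

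**Conclusion.** The concern holds and should be fixed. The clear defect is at rest: the planned comparison omits group and so cannot test (c). For task fMRI the interaction is implied at most, and for EEfRT the role of condition is unspecified. The period term is missing throughout, usually at small cost.

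The size rests on assumed responses, since the document gives none. Under equal responses of 0.5 to 0.6 SD, the resting-state test is significant in 93% to 99% of trials with (c) false. The correct test has much less power: at 25 v 25 it needs a group difference of 0.81 SD for 80% power, before any FDR adjustment. That is a limitation to state, not a reason to test a different question.

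**What to change.** In Section 6, for the resting-state, task-fMRI and behavioural EEfRT outcomes at Visits 2 and 3, specify a GEE clustered on participant with group, condition, group x condition and period, plus the covariates already planned. In the two imaging models, name group x condition as the test of hypothesis (c). From the same EEfRT model, report the patient-control difference under each condition beside the averaged one. State the detectable interaction for the sample size and split finally adopted.

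This changes wording and needs no new data. The costs are:

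- The period term takes about 1 point of power at 25 v 25 if there is no period effect, and under 0.5 point at 58 or 75 per group.
- The interaction has lower power than the condition effect, and the plan must say so.
- The placebo-session EEfRT contrast is less precise than the averaged one. The SE ratio is 1/√((1 + ρ)/2), so the SE is about 8%, 15% or 24% larger at assumed within-person correlations ρ of 0.7, 0.5 or 0.3.

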Genes that were differentially expressed between groups were selected for mediation analyses. Diagnosis by BMI effects on expression of dopamine genes were fully mediated by expression of INSR. Analysis of conditional indirect effects showed interactions between INSR and BMI, indicating significantly stronger indirect effects at higher BMI values. In the hippocampus, we observed that expression of insulin receptor substrate 1 and 2 fully mediated the effects of diagnosis on expression of dopamine genes (Figure 2). All models were significant (e.g. DRD1: $R^2 = 0.31$, $F_{6,385} = 29.519$, p < 0.001). These results suggest that the differential expression of dopamine-related molecules in the postmortem brain of individuals with mental disorders is related to altered expression of insulin signaling genes. We also observed that obesity has region-specific moderating effects on gene expression and co-expression, supporting the hypothesis that metabolic systems are critical mediators of dopaminergic function and providing the rationale for further investigation.

Figure 1 – Mean standardized expression values of insulin and dopamine signaling genes in the dorsolateral prefrontal cortex, according to group (HC vs. MI) and obesity (BMI \geq 30 kg/m²). HC: healthy controls; MI: mental illness; BMI: body mass index.

[figure not shown]
[figure not shown]

Figure 2 – Unstandardized path coefficients for a mediation model in the hippocampus, adjusted for age, gender, race, ethanol and nicotine/cotinine. * p < 0.05; ** p < 0.001.

[name] Research Proposal Project Title: Anhedonia and the insulin pathway: a mechanistic nexus for the mood and metabolic disorders comorbidity

3. Design and Methodology

Study population: We propose to recruit 50 adults between the ages of 18 to 50 years: 25 patients with DSM-5 defined MDD or BDI/II, in a depressive episode, recruited from the Mood Disorder Psychopharmacology Unit, University Health Network, and 25 age- and sex-matched healthy controls recruited through local advertisements in the community.

Inclusion criteria (patients):

- 1. Age 18-50
- 2. DSM-5 defined MDD/BD and a total score ≥20 on the Montgomery-Åsberg Depression Rating Scale (MADRS) and no history of dementia or intellectual disability
- 3. A written, voluntary informed consent prior to study enrollment

Exclusion criteria (patients):

- 1. Use of insulin and/or oral hypoglycemiants, due to its confounding effects

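### The plan states both 50 and 150 participants, names two different primary hypotheses, and lists no assay for the molecular aim or the dopamine mediator

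*Combined protocol and SAP*

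**What the plan says.** **Sample size.** Section 3 (Study population): "We propose to recruit 50 adults between the ages of 18 to 50 years", split 25 patients and 25 matched controls. Section 3 (Study Procedures) repeats 50 for the cross-over. Section 6 (Power Analysis) gives 116 for 80% power and an enrolment goal of 150. Section 6 (Potential Challenges) again works with 150 and plans a preliminary look at 50, described as a third of the total.

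**Primary hypothesis.** Section 1: "we primarily hypothesize that individuals with mood disorders will display decreased willingness to make effort for rewards, relative to healthy controls". It expects this deficit to go along with molecular, physiological and neural insulin measures. Section 6 (Power Analysis): "The primary hypothesis of this study is that anhedonic symptoms in individuals with mood disorders will be mediated by abnormalities in insulin signaling". The Analytic Plan in Section 6 also puts mediation first. Its outcome Y covers both anhedonia and reward behavior, and its mediator M covers insulin signaling and dopamine metabolism. Section 3 (Behavioral assessment) adds: "The primary behavioral measurement will be effort-based decision-making", measured with the EEfRT at Visits 2 and 3.

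**Assays.** Aim (a) in Section 1 is to be met "using a proteomics and gene expression approach". Section 3 and Table 1 list lipids, insulin, glucose, HbA1c, C-peptide, IGF-1, thyroid tests, CRP and hCG, with HOMA-IR, TNF markers and an inflammatory cytokine panel. Of the blood samples, Section 3 (Biomarkers) says "plasma will be stored at -80" °C.

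**The concern.** The only power statement belongs to a sample two to three times the one described in the design section. If 50 is the real number, the 80% is not delivered and a null mediation result would say little.

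The documents also leave open what the trial's main answer is. A group difference in effort and an indirect effect on anhedonic symptoms are different quantities on different outcomes, and the same data could support one and not the other. Neither Y nor M is tied to one named variable, so that choice stays open too.

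Finally, a mediator and an aim that nothing in the schedule measures cannot be analysed as written.

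**Working it through.** **1. Inputs.** Paths of about 0.25 to 0.35, 80% power, N = 116 and enrolment of 150 (Section 6, Power Analysis). Bias-corrected bootstrap test with 95% interval (Section 6, Analytic Plan); two-sided 5% is inferred from that interval because the power paragraph states no alpha. 25 + 25 (Section 3). Assumptions added here: standardized betas, no direct effect, no covariates.

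**2. Simulation.** X is a balanced two-group variable scaled to variance 1; M = aX + √(1−a²)·e₁; Y = bM + √(1−b²)·e₂. The indirect effect is the product of the estimated a and b. The interval runs between the bootstrap quantiles at Φ(2z₀ ± 1.96), where Φ(z₀) is the share of bootstrap values below the estimate. There were 2000 data sets per cell and 800 resamples; Monte Carlo SE is at most 1.1 points.

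| a, b | N = 116 | N = 50 | N = 150 |
|---|---|---|---|
| 0.25, 0.25 | 68.4% | 25.2% | 81.9% |
| 0.25, 0.35 | 82.3% | 40.5% | 89.6% |
| 0.35, 0.25 | 78.0% | 36.6% | 86.6% |
| 0.35, 0.35 | 96.1% | 58.9% | 98.9% |

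The plan's 116 is reproduced for one path at 0.25 and one at 0.35 (78% to 82%). It falls short if both are 0.25. Other scalings of X and of the residuals gave 23% to 59% at N = 50, so the result does not hinge on that choice. For 80% power at N = 50 with equal paths, each would need to be about 0.42 (79.8%), above the plan's range.

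**3. Closed-form cross-check.** Joint significance: power ≈ Φ(atanh(a)·√(n−3) − 1.96) × Φ(atanh(b)·√(n−4) − 1.96). For 0.25 and 0.35:
- n = 116: 0.775 × 0.972 = 0.753
- n = 50: 0.417 × 0.698 = 0.291

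This test is more conservative than the bootstrap, but the drop is of the same order.

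**4. Effort difference.** Two-sample t-test standing in for GEE, 5% two-sided, 80% power. The normal approximation at 25 + 25 is (1.960 + 0.842) × √(2/25) = 0.79 SD. The exact t values are 0.809 SD (25 + 25), 0.525 SD (58 + 58) and 0.460 SD (75 + 75). The documents give no EEfRT effect size to compare with these.

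**5. Which size governs?** Section 7 allows 27 months at 2 to 3 participants per site per month: 27 × 2 = 54 to 27 × 3 = 81 per site, or 108 to 162 for two sites. One site fits 50; two sites could reach 150. The number of sites is not settled: Study population names one recruiting unit for patients, while Section 6 speaks of clinics in the plural.

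**6. Source of the betas.** Section 2 derives them from post-mortem tissue, with insulin-gene expression as mediator and dopamine-gene expression as outcome, in patients who include psychotic disorders. The Figure 2 caption reads "Unstandardized path coefficients for a mediation model in the hippocampus", so treating them as standardized is itself an assumption.

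**7. The two primaries side by side.**

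| | Section 1 | Section 6, Power Analysis |
|---|---|---|
| Outcome | effort for rewards | anhedonic symptoms |
| Quantity | patient-control difference, with associations | indirect effect through insulin signaling |
| Powered | no | yes, 116 |

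The EEfRT is run only after a spray, and no section says whether the insulin session, the diluent session or both supply the patient-control contrast.

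**8. Assay check.** None of the items listed in Section 3 and Table 1 measures dopamine metabolism, gene expression, or PI3K/Akt or Ras/MAP kinase proteins. The multiplex panel is inflammatory. Plasma is stored, but no such assay is assigned to it.

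**The case against.** **A reader might infer that the trial is shown to be underpowered.** The documents do not support that. The 150 is current text and covers 116. The design section also calls the imaging participants a subsample, which allows a reading in which 50 are scanned within a larger cohort. Against that reading, Study population gives 50 as the whole recruited group, and Table 1 is the only visit schedule. What stands is a contradiction, with a power loss that follows only if 50 governs.

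**A reader might take 37% to 41% as the trial's likely power.** It is not. The betas describe gene expression in post-mortem brain, not a peripheral insulin measure and an anhedonia score. The percentages show only what the plan's own inputs imply.

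**The hypotheses overlap.** Section 1 pairs the effort deficit with insulin measures, and Y in the Analytic Plan includes reward behavior. Calling the EEfRT the primary behavioral measure ranks it among behavioral measures and does not create a third primary hypothesis. This is fair. The firm conflict is between Section 1 and the Power Analysis, and it remains because both outcome and quantity differ. The false discovery rate rule sits in the imaging paragraph and does not settle which outcome is primary.

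**A reader might infer that the mediator cannot be measured at all.** Insulin, HOMA-IR, C-peptide and IGF-1 give a peripheral proxy for its insulin part. The gap is limited to dopamine and Aim (a). A part of the document following the Section 8 heading (Personnel and Facilities) was not available, so an assay described there cannot be excluded.

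**Conclusion.** The point holds in three parts.

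1. The sample size is unreconciled. The 116 is sound for mixed paths on its own inputs and 150 would cover it. If 50 governs, mediation power is about 25% to 60% (about 37% to 41% for mixed paths) against the stated 80%, and the detectable effort difference is about 0.81 SD. This rests on standardized betas, no direct effect, no covariates, and a t-test in place of GEE.
2. Section 1 and the Power Analysis name different primary hypotheses, and only mediation is powered.
3. In the text supplied, the dopamine part of M and the whole of Aim (a) have no assay.

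This should be corrected before analysis, because the main question, its outcome and its sample size are all unsettled. Parts 2 and 3 do not depend on any of the power assumptions.

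**What to change.** - **Sample size.** State one number in Section 3 (Study population and Study Procedures) and Section 6 (Power Analysis and Potential Challenges). Say that 116 for 80% applies only to the mediation test. Restate mediation power, and give the detectable effort difference, at the size actually used. If that is 50, withdraw the 80% claim.
- **Primary hypothesis.** Declare one, with one named outcome and, if mediation is chosen, one named and measured mediator. Word it identically in Section 1 and in both places in Section 6. The choice is the sponsor's; at 50, the low mediation power should be weighed in making it.
- **EEfRT.** Name the session or sessions used for the patient-control contrast.
- **Molecular part.** Remove dopamine metabolism from M, and state that no conclusion will be drawn on hypothesis (a) or Aim (a), unless an assay, a sample and a visit are named.

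**Cost.** Protocol and SAP wording, with no new data needed. The stated power becomes less favourable if 50 governs. Aim (a) yields no conclusion unless assays are named, which would add laboratory work and possibly samples.
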